# 3. Primary objective: Effectiveness of ITAMITED as it is applied routinely in its natural context.

We will analyse effectiveness with three complementary analyses performed for data/analysis tranches 2 and 3.

(a) Baseline/termination change. This is has been the traditional focus of many existing explorations of effectiveness of treatment. We will report both mean change and also effect sizes reporting Cohen's d2 and dz (Cohen, 1988) (the ratio of mean change to baseline SD and the ratio of mean change to SD of change respectively) and report these with bootstrap CIs. As well as reporting the global aggregate mean shifts with bootstrap 95% CI for each score. We will report the regression of termination scores on baseline scores and the distributions of change scores.

We will explore the impact of baseline variables: gender, age, diagnosis, demographic

variables, medication use and service on change. These predictor effects will be explored entering them as predictors of termination scores/values in ANOVA models with attention paid to the almost certain violation of assumptions of the ANOVA and exploration of mitigation of those violations. As gender and age are such crucial variables in Eating Disorders (Eds) the effects of entering these as predictors (or analysing separately be gender) on effects of other variables will be reported.

To address individual change we will report the Jacobson plot of termination against baseline scores for all scores and report the RCSC breakdown of change on each measure where it is possible to define the CSC and RCI.

(b) Multilevel models (MLM) of rates of change. MLM allows analysis of change slopes across diverse durations of therapy/ascertainment and the method handles the nonindependence of observations arising from the repeated measures within participant appropriately. These analyses can give a much more nuanced picture of change than baseline/termination analyses while allowing exploration of the effects of the same predictors and covariates analysed in (a). As for (a), durations of therapy are not directly reflected in the analyses though in contrast to (a), all data across all durations of data collection are used rather than just the first and last values.

We will analyse fit to linear, square root and log-linear transforms of time as these have been the most widely reported linearised change/time patterns in the literature. The analyses against the baseline predictors (as fixed predictors) noted above allow some exploration of heterogeneity of change trajectories against those measured variables. Diagnostics after overall MLM analyses will be considered with the earlier analyses (i.e. tranche 1 baseline analyses, and baseline/termination analyses from tranche 2 above) as possible indicators of subgroups differing fundamentally in pertinent statistical characteristics. These subgroup indications will inform analyses exploring these subgroups as possible indicators of mixture model population structures of change.

However, heterogeneity may also relate to variables not measured in this study. (There are a very large number of such potential predictors, no realistic study can measure them all.) In order to explore possible heterogeneity other than arising from measured predictors we will conduct two other analyses of change trajectories relating to MLM estimation: latent profile analysis (LPA) of change and nearest neighbour prediction of change.

There are two complicating issues that will have to be considered here. The first is that not all centres were active at the start of data collection so analysis will be checked for any impacts of this, i.e. confounding by centre. The other challenge arose from the coronavirus pandemic. Social distancing regulations forced all but inpatient therapy to online therapy for (currently one) period in 2020. Time profiles will be inspected carefully against dates as well as against time in therapy to check on the impacts of this and in order to decide how best to prevent this creating artefactual impacts on trajectory analyses.

(c) Survival analysis (e.g. Allgulander & Fisher, 1986; Singer & Willett, 2003; Willett & Singer, 1993)for time to terminations by category of termination. These analyses focus on the time spans between entry into treatment and termination which are not so focal in (a) and (b). The particular strength of survival analysis for a naturalistic cohort follow-up study is that it address the inevitable right censoring of follow-up. That is that at termination of intensive data collection some participants will be still in treatment so their "outcome" is only know to this point and how long each has been in treatment to that point will be very varied with some of the very first participants joining the study potentially still in treatment near three years on though many of those early participants will have terminated treatment so not be "right censored". Of course far more of the recently recruited participants will be still in treatment and their change only known to that point.

The uncertainties arising from this censoring of outcomes is considered in, and visible in, the findings of survival analyses. We will analyse time to completion of therapy by category of termination and also analyse how baseline predictor variables impact on the slope of those curves. Different survival analytic methods make different assumptions about the relationships between predictors and the time curves, notably whether there is "parallelism" of curves across groups, or not, and these issues will be explored, and the appropriate analyses reported.

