hunting/hacking" with the considerable risk of severely misleading findings. We recognise the multiple tests issue and wish to conduct analyses as likely to result in replicable findings as possible. We also see the only protection against the accusation of p-value hunting/hacking is to be as clear as possible about the distinction between planned, i.e. a priori analyses, and "emergent" ones, i.e. those conducted in exploration of, and intended to throw more light on unexpected findings. With a very complex clinical service, multiple important aims and an extensive dataset, there are an almost infinite number of possible analyses and a very large number of important analyses apparent *a priori*. This makes it challenging even to summarise the planned analyses; hence the length of this, Data Analysis Plan (DAP) which is itself a shortened "freeze" of a much larger document. This document is being submitted with the study protocol paper and designed to complement that and enable a moderately thorough coverage of the *a priori* analyses and the methodological/statistical issues that would otherwise overwhelm the paper. In line with our epistemological position, this document has been written trying to be readable to research interested clinicians as well as clinical researchers, the target context for findings, not for statisticians and many technical statistical issues are presented as simply as possible.

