#### 2. Planned and emergent analyses

Many analyses will be conducted to address the study objectives and these are summarised below. As noted, the complexity of the data will certainly lead to the performance of emergent analyses. These will always be defined as such, against this DAP, in any presentations, reports or papers. All publications will be made with the (Altman & Moher, 2013) transparency statement which will apply to the distinction between *a priori* and emergent analyses as much as to all important issues to be acknowledged transparently.

The analysis timing has been designed in three tranches.

- The first tranche will focus on the baseline data for participants recruited during the first three years. The most important focus will be to establish the baseline distributions of variables that will be used later to measure change, the psychometric properties of

those measures, the differences between clinical centers, and any strong associations between baseline variables likely to raise issues about confounding in the subsequent analyses of change.

- The second tranche will contain all data collected by the end of October 2020: the endof the intensive data collection phase. When analysing these data, the focus will be on change: changes in sociodemographic variables (assessed annually) and clinical interventions but primarily changes in the key clinical outcome variables of the questionaire scores and BMI.
- The third tranche will add the follow-up information for all the participants recruited to October 2020 as and followed-up, where in continued clinical contact with the services, to November 2025. The main analyses for this tranche will largely follow the explorations of change, its diversity and its predictors as from the second tranche.

Here we present the a priori analyses planned for each objective and broken down by tranche.

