# Secondary objectives:

### 1. Describe the study participants.

To establish the baseline distributions of variables (i.e., BMI, CORE, EAT-26/ChEAT-26, and BITE) that will be used later to measure change (tranche 1). The aims are:

- To describe the distributions of scores at baseline on the change measures and how these relate to other variables:
  - demographic variables, primarily age and gender;
  - o clinical variables primarily diagnosis, care type and medication and,
  - both because of the interest in this within ITA, and for the MLM analyses
    of change (above) and the differences between clinical centres.

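### The predictor models in analysis (a) aim at change, but the model as written has the termination score as response and states no baseline term

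*SAP*

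**What the plan says.** SAP section 3 (Primary objective), analysis (a), headed baseline/termination change, gives the aim of its predictor analysis in one sentence: "We will explore the impact of baseline variables: gender, age, diagnosis, demographic", continuing "variables, medication use and service on change". The next sentence gives the model: "These predictor effects will be explored entering them as predictors of termination scores/values in ANOVA models". The only further terms discussed are gender and age, because of their importance in eating disorders.

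The paragraph before has a separate reporting item: "We will report the regression of termination scores on baseline scores and the distributions of change scores". No sentence links that regression to the predictor models, and no later section adds a baseline term to them.

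Elsewhere the SAP treats baseline differences as an open question:
- Section 2 (Planned and emergent analyses) has the first tranche look for "any strong associations between baseline variables likely to raise issues about confounding in the subsequent analyses of change".
- Secondary objective 1 plans "To describe the distributions of scores at baseline on the change measures and how these relate to other variables". These include age, gender, "clinical variables primarily diagnosis, care type and medication", and clinical centre.
- Secondary objective 2, on internal reliability, cites evidence that score distributions can differ by gender and age through adolescence.

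**The concern.** The stated target is change, while the stated response is an end level. In a randomised comparison the two would differ little on average. Here the groups are defined by patient characteristics, treatment and service, and nothing balances their starting scores. Fitted literally, the model would credit a predictor with an effect on change when one group simply starts worse and both groups change by the same amount. It could equally hide a real difference in change that runs against the baseline gap.

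The baseline descriptions planned for the first tranche would make such a gap visible, but would not remove it from the model. The results of (a) also have some influence downstream: under (b), the baseline/termination analyses are among the sources used to suggest subgroups for later modelling.

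**Working it through.** **Inputs.** The plan states no figure for this analysis, so there is none to reproduce. It gives no baseline gap, baseline-termination correlation or group size. The check is therefore algebraic and uses no assumed numbers.

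**Notation.** For one measure, let B be the baseline score, T the termination score and C = T − B the change. For a two-level predictor, write ΔB, ΔT and ΔC for the differences in group means, all in the same participants.

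**Step 1: the identity.** Since T = B + C for every participant,

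ΔT = ΔB + ΔC.

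The same holds term by term with several predictors. Least-squares coefficients are linear in the response, so each predictor's coefficient for T is its coefficient for B plus its coefficient for C.

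**Step 2: three candidate models.** Let b be the pooled within-group slope of T on B. Each model estimates ΔT − k·ΔB, with a different k:

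| Model | k | Group effect |
|---|---|---|
| Termination score only (literal reading) | 0 | ΔC + ΔB |
| Termination score with baseline as covariate | b | ΔC + (1 − b)ΔB |
| Change score as response | 1 | ΔC |

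**Step 3: special cases.**
- No baseline gap (ΔB = 0): all three models give ΔC, and the wording does no harm.
- Equal mean change (ΔC = 0): the models give ΔB, (1 − b)ΔB and 0, in the order of the table. The literal model reports the whole baseline gap as an effect on change.
- No difference at equal baseline (ΔT = b·ΔB): they give b·ΔB, 0 and −(1 − b)ΔB.

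**Reading.** As a measure of difference in mean change, the termination-only model is off by exactly ΔB. The other two answer different questions: the difference expected at equal baseline, and the difference in mean change. They differ from each other by (1 − b)ΔB, so they can disagree whenever the groups start apart and b is not 1. The termination-only model answers neither question unless ΔB = 0 (or, for the equal-baseline question, b = 0).

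**The case against.** The strongest reply is that baseline is meant to be in the model. Analysis (a) is headed as baseline/termination change. The regression of termination on baseline comes shortly before the predictor models, and entering predictors of termination scores can be read as adding terms to it. Analysis (b) describes (a) as using the first and last values, and speaks of covariates as well as predictors in (a). This makes the baseline-inclusive reading plausible. It does not state it: the remark about first and last values concerns (a) as a whole, and the covariates may be just gender and age.

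A second reply is that the SAP is a shortened, deliberately simple extract of a larger document, written to accompany a protocol paper, and calls its methods exploratory and descriptive. The full terms may be set out in documents not seen here. That lowers the weight of the point, but the missing term takes only one plain clause.

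A third reply is that little depends on it. Secondary objective 3 places change patterns by predictors in the multilevel models, and (b) examines the same predictors there. This stands, and confines the problem to the predictor part of (a).

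A reader might infer more than the text supports:
- *That the effectiveness estimate is biased.* It is not affected; mean change and its effect sizes do not use these models.
- *That the plan itself predicts large baseline gaps for these predictors.* The strong statement about severity, under secondary objective 4, concerns care type. Care type is not in the list in (a), and it is to be studied largely through baseline/termination change.
- *That the wording breaches the plan's own safeguard, "the only protection against the accusation of p-value hunting/hacking is to be as clear as possible about the distinction between planned".* That passage is about separating planned from emergent analyses. It does not address how fully each model is specified.
- *That a particular false-positive rate follows.* Any such rate would rest entirely on an assumed gap, correlation and group size.

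**Conclusion.** The point holds as a gap in the specification. The aim is change, the written response is the termination score, and no baseline term is stated. On the literal reading the predictor effect differs from the difference in change by exactly the baseline gap, and by nothing if there is no gap. This rests on the identity alone; its size in this study cannot be given from the SAP. The text does not show that baseline will be omitted, and if it is included the misattribution for the equal-baseline question goes away. Mean change, d2/dz, the reliable and clinically significant change breakdown, the Jacobson plot and the multilevel estimates are untouched. Severity is minor to moderate: a cheap improvement to the wording.

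**What to change.** In the model sentence of section 3(a), after the words saying that the predictors are entered, insert: *together with the baseline value of the same measure*. Then add two short statements:

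1. The model with change score as response will be reported as a sensitivity analysis. The baseline-adjusted model addresses the difference at equal baseline and the change-score model the difference in mean change, and the two can disagree when groups differ at baseline.
2. A model of termination scores without baseline will not be interpreted as an effect on change.

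The cost is a few sentences and one extra set of models. No new data are needed, since mean change in (a) already requires the baseline value. The downside is that baseline adjustment is open to measurement error in the baseline score, so some of a baseline gap may remain in the adjusted effect. Change scores in turn are open to regression to the mean, which is a further reason to show both.

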### 1. Multiple tests and p-value hunting/hacking

We recognise that there are no perfect ways of exploring such data. There are many areas where exploration of associations, e.g. between plausible predictor and response variables can usefully be informed by null hypothesis testing. As there are many such associations, this raises the classical "multiple tests" issue: that if all the null hypotheses about the population were true (and independent) then the expectation of a single test being "significant" at the alpha level (.05) rises rapidly, and markedly above .05, as the number of tests rises. This issue has of course been know from the invention of hypothesis testing, for a readable early discussion in relation to mental health research see (e.g. Grove & Andreason, 1982). This leads to two related issues: the simple one of the elevated "studywise" false positive rate, and the issue of "p-value hunting/hacking" (touched on as part of the recent resurgence of interest in trying to reduce the dangers of naïve use of hypothesis testing, e.g. (Amrhein et al., 2019; APA, 2016; Wasserstein & Lazar, 2016).

There is an extensive literature with arguments for and against application of methods to reduce the overall "studywise" false positive rate to .05, and various methods by which to do this (Primo de Carvalho Alves & Sica da Rocha, 2019 e.g.). Given the diversity of areas in which we will be exploring associations and where null hypothesis significance testing (NHST) has some value as a decision rule, we do not propose to use any of the methods of controlling for the inevitably elevated false positive rate. However, we do propose to be consistent and clear in recognising the risk. All hypothesis tests will be reported with the actual p value, not as "p < .05" versus "NS" (or some other ordinal categorisation of p values by asterixes). Where possible, 95% confidence intervals (CIs) will be reported for all statistics. To be precise, we will report the Bias Corrected Adjusted, (bca) 95% CI from 1000 bootstrap replications unless it is not available in which case the percential CI will be used, see (Carpenter & Bithell, 2000; Puth et al., 2015).

That issue of the inflated type I error rate that is bound to arise from there being multiple questions of interest leads to the option for deliberate or uninformed "p-value

© CE & CP for ITAMITED group

Page 2 of 14

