As well as within-measure analyses, we will also conduct across-measure factor analyses as these allow construct validity to check on where one might expect shared factor structure (i.e. for (Ch)EAT and BITE) or might expect largely unrelated factor structure (i.e. between (YP-)CORE and both (Ch)EAT and BITE). These analyses will be CFA by design structure and EFA if fit to design structure is clearly very poor.

- If some measures/scores show clear fit to unidimensionality, we will conduct Item Response Theory (IRT) analyses to identify cutting points and potential evidence that the conventional scoring of the measures may be suboptimal for cross-sectional comparisons.
- Convergent validity between related measures (EAT-26/CHEAT-26 and BITE) and convergent and divergent validity between them and diagnoses and BMI. These are more conventional explorations than the item level across-measure factor analyses noted above. We will explore scatterplots for marked non-linearity or

clearly non-zero intercepts and, assuming there are not major issues of those kinds, will report Spearman rho and Pearson R correlations with bootstrap confidence intervals. Reporting both correlations maximises comparability with existing literature as Spearman correlations have often been reported in the past, before the widespread availability of bootstrapping, as score distributions are generally not Gaussian. If numbers allow (n > 80) separate analyses will be conducted by gender, age and diagnosis.

Divergent validity/confounding against gender, age, first language, education.
 Distributions will be compared by groups (with sensible age groups) and the simple scattergrams against age inspected. Unless clearly inappropriate Pearson correlations with age, and mean differences by groups, will be reported with bootstrapped CIs.

To explore the psychometrics of change (tranche  $\underline{2}$  and  $\underline{3}$ ):

- Where participants have sufficient completed measures (n > 20) we will to apply P-technique estimation of Cronbach's alpha within individuals, within and across measures. For the small number of participants with the larger number of sufficient completions (n > 40) we will also explore P-technique "factor" structure (actually Principal Component Analyses (PCA)) to show the structures that emerge where the sequences of completed measures within individuals allow this.

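### Analysis (a) provides for a split by gender but plans no gender-by-predictor interaction estimate and sets no minimum group size, so an effect can look gender-specific through unequal precision alone.

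*SAP*

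**What the plan says.** Under *3. Primary objective*, part (a), the SAP lists baseline variables whose influence on change will be studied: gender, age, diagnosis, demographic variables, medication use and service. The method is stated as "These predictor effects will be explored entering them as predictors of termination scores/values in ANOVA models". For gender and age it adds that "the effects of entering these as predictors (or analysing separately be gender) on effects of other variables will be reported". Covariate entry comes first and the split by gender is a bracketed alternative. No interaction of gender or age with another predictor is named, and no group size is required before splitting.

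Under *Secondary objectives, 2. Study the psychometric properties of the self-report measures*, the convergent-validity correlations follow a similar pattern: "separate analyses will be conducted by gender, age and diagnosis", but there only if numbers allow (n > 80). The factor analyses in the same section carry a threshold of n > 250 and are followed by a between-group invariance analysis that includes gender.

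The general rules are in *1. Multiple tests and p-value hunting/hacking*. Exact p values replace a significant/NS split, and "Where possible, 95% confidence intervals (CIs) will be reported for all statistics". Hypothesis testing is nevertheless kept for areas "where null hypothesis significance testing (NHST) has some value as a decision rule".

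**The concern.** Two different questions can be asked about gender. The first is whether the effect of, say, diagnosis on termination score changes once gender is allowed for. Entering gender as a predictor answers that. The second is whether the effect of diagnosis differs between genders. Splitting the data invites that question but does not answer it: each half has its own estimate, interval and p value, and nothing measures the distance between them.

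A reader shown a narrow interval excluding zero in one gender and a wide interval including zero in the other may conclude that the predictor works in one gender only. The same picture arises when the effects are identical and one group is small.

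This matters for later work too. Part (b) of the primary objective says that the baseline/termination analyses will be considered as possible pointers to subgroups that differ in kind, and that such pointers will inform mixture-type modelling of change. Under *2. Planned and emergent analyses*, an interaction added after the split results have been seen would have to be labelled emergent.

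**Working it through.** **Figures in the plan.** The SAP gives no sample size, gender split, effect size or power, so there is no figure to reproduce. From the SAP come alpha = .05 (*1. Multiple tests*) and the n > 80 threshold for correlations. Two-sided testing, the gender shares, power and correlations below are assumptions.

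**Step 1: same true effect in both genders.** Let s be the smaller gender's share and P the power in the larger gender.

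- Expected z in the larger group: λ₁ = 1.96 + z(P).
- Expected z in the smaller group, with the same effect and SD: λ₂ = λ₁ × √(s/(1−s)).
- Probability of p < .05 in group i: Pᵢ = 1 − Φ(1.96 − λᵢ) + Φ(−1.96 − λᵢ).
- Probability of p < .05 in exactly one gender: D = P₁(1−P₂) + P₂(1−P₁).

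Worked case, P = 90% and s = 10%: λ₁ = 1.96 + 1.282 = 3.242; λ₂ = 3.242 × √(0.1/0.9) = 1.081; P₂ = 0.191; D = 0.9 × 0.809 + 0.191 × 0.1 = 0.747.

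| Power in larger gender | s = 10% | s = 20% | s = 30% | s = 40% | s = 50% |
|---|---|---|---|---|---|
| 80% | 0.71 | 0.63 | 0.53 | 0.42 | 0.32 |
| 90% | 0.75 | 0.61 | 0.45 | 0.30 | 0.18 |
| 95% | 0.75 | 0.56 | 0.36 | 0.20 | 0.10 |
| 99% | 0.70 | 0.43 | 0.21 | 0.07 | 0.02 |

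For a 10-20% share and 80-95% power the range is 0.56 to 0.75. With no true effect, D = 2 × 0.05 × 0.95 = 0.095.

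**Step 2: dependence on effect size.** Take 270 and 30 participants and the same true correlation r in both. With Fisher's z, λᵢ = atanh(r) × √(nᵢ − 3).

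| r | P₁ (n = 270) | P₂ (n = 30) | D |
|---|---|---|---|
| 0.1 | 0.37 | 0.08 | 0.40 |
| 0.2 | 0.91 | 0.18 | 0.76 |
| 0.3 | 1.00 | 0.36 | 0.64 |
| 0.4 | 1.00 | 0.60 | 0.41 |
| 0.5 | 1.00 | 0.81 | 0.19 |

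Of these five values, r = 0.2 gives the highest discordance.

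**Step 3: groups that just pass n > 80.** If the threshold is read per group, take 81 in the smaller group and 400 in the larger. D is 0.57 at r = 0.2, 0.22 at r = 0.3 and 0.04 at r = 0.4. The threshold helps a good deal for strong correlations but does not remove the problem for weak ones.

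**Step 4: what an interaction estimate would do.** A test of the difference at .05 would wrongly declare identical effects different in 5% of data sets, by construction. Its interval would also show how little is known. At 270 and 30, the 95% half-width for the difference in Fisher z is 1.96 × √(1/267 + 1/27) = 0.40.

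**The case against.** The strongest reply is that the sentence is about adjustment. It promises to report how other effects move when gender and age are entered, and the split is a bracketed alternative. A reader might infer that gender differences are going to be decided by comparing the two p values. The SAP does not say so, and its general rules point the other way: "All hypothesis tests will be reported with the actual p value, not as 'p < .05' versus 'NS" rules out the ordinal reading, and intervals are promised as well. This stands. What it does not supply is the missing quantity: two intervals side by side are not an interval for the difference.

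A second reply is that the convergent-validity correlations are protected by n > 80, and that between-group work is planned elsewhere (measurement invariance by gender, and mean differences between groups with bootstrapped CIs). This also stands in part. If n > 80 is meant per group, a group of 30 would not be split off there, so the high figures in Step 2 cannot be carried over to those correlations. Part (a) has no such threshold, and neither of the other analyses compares correlations or predictor effects between genders.

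A third reply is that the SAP describes itself as shortened from a much larger document, and that its ANOVA models do not exclude interactions. That is fair, but this is the document against which analyses will be classed as planned or emergent, so an interaction not named here is at risk of counting as emergent.

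A reader might also infer that testing everyone and then each gender roughly doubles each predictor's false-positive rate. The SAP does not support that as a finding. It offers the split as an alternative, so three tests per predictor are not established, and it openly accepts the inflation: "we do not propose to use any of the methods of controlling for the inevitably elevated false positive rate".

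**Conclusion.** The point holds in a limited form. Part (a) provides for a split by gender with no estimate of how far effects differ and no minimum group size, so apparent gender-specificity can come from unequal precision.

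The size is conditional. The 56-75% range assumes identical true effects, a smaller gender of 10-20%, 80-95% power in the larger, and a reader who contrasts p < .05 with p > .05. It is not a general rate: at a 40% share with 95% power it is 20%, at r = 0.1 with 270 and 30 it is about 40%, and at r = 0.5 it is 19%. Since the SAP gives none of these inputs, it cannot be said that identical effects will usually look different. This is a cheap improvement to an exploratory plan; it does not invalidate the primary analysis.

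**What to change.** In *3. Primary objective*, part (a), state that wherever predictor effects are given by gender, the gender × predictor term will be fitted in the same model (and age × predictor where effects by age are of interest). Report the interaction estimate with its 95% bootstrap CI, and present gender-specific estimates with their CIs as descriptive.

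In *Secondary objectives, 2*, where groups pass n > 80 and are analysed separately, also report the difference between the group correlations with its bootstrap CI.

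The cost is about one sentence in each place and one extra model term per predictor. The intervals will be wide when one gender is small, and the report must say that such data can neither establish nor exclude a gender difference.
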